#### 8.2.1. Work Productivity and Activity Impairment

The following endpoints will be derived and summarised by treatment group and visit for the ITT population. Change from baseline will also be derived and summarised.

Endpoint	Derivation
Percentage work time missed due to health	$Q2 / (Q2 + Q4)$
Percentage impairment while working due to health	$Q5 / 10$
Percentage overall work impairment due to health	$Q2 / (Q2 + Q4) + [(1 - (Q2 / (Q2 + Q4))) \times (Q5 / 10)]$
Percentage activity impairment due to health	$Q6 / 10$

No statistical analysis of work productivity and activity impairment will be performed.

## 9. POPULATION PHARMACOKINETIC ANALYSES

Refer to Data Display Standards & Handling Conventions (Section [16.5.3](#) Reporting Standards for Pharmacokinetic Data).

In support of the analysis described below, a specific dataset will be generated. Specifications for the generation of the dataset will be provided in a separate document.

Details of the planned displays are provided in [Appendix 10](#): List of Data Displays and will be based on GSK Data Standards and statistical principles.

### 9.1. Population of Interest

The population PK analysis will be performed on the PK population.

### 9.2. Strategy for Intercurrent (Post-Randomization) Events

For subjects withdrawing prematurely from study treatment, all available data will be included in the analysis.

Based on mepolizumab PK knowledge, concentrations below the limit of quantification (BLQ) of the assay is considered unlikely at the 300 mg SC dose investigated, in view of the PK sampling scheme selected in the study. Thus, any such results will be treated as missing.

Outlier data will be assessed for plausibility; however, the aim is to use all available data whenever possible. Any decision to exclude data will be fully documented and specified in the clinical study report.

### 9.3. Population Pharmacokinetic Methodology

Sparse blood sampling is implemented in this study for determination of mepolizumab plasma concentration and subsequent data analysis by population PK methods using the most recent population pharmacokinetics model (meta-analysis PK model of data across indications described in GlaxoSmithKline Document Number [2015N238436\\_00](#)). Since mepolizumab PK following intravenous administration in HES subjects has already been evaluated within the population PK meta-analysis (using PK samples collected in previous Phase III study MHE100185), the main objectives of this population PK analysis are:

- To evaluate mepolizumab pharmacokinetics in subjects with HES following the subcutaneous administration of a 300 mg dose every 4 weeks.
- To investigate the impact of covariates of interest in the studied HES population (such as baseline characteristics, co-medication) on specific parameters (e.g. clearance) in order to identify potential sources of inter-individual variability in these parameters.
- To obtain individual plasma concentration predictions for the timepoints at which PD is measured to allow the conduct of population PKPD analyses if deemed appropriate.

Mepolizumab plasma concentration-time data (samples collected at Weeks 4, 16 and 32; at the early Withdrawal and the additional follow-up visits (if applicable)) will be analysed by population methods using nonlinear mixed-effects modelling. The analysis will be carried out using appropriate software (e.g., NONMEM or SAS).

### 9.3.1. Base Model

In consideration of the sparse sampling (3 samples post-start of treatment over 32 weeks: Week 4, 16 and 32) and the wealth of mepolizumab PK knowledge, the most recent population PK model will be applied directly to the dataset without estimation (e.g.  $\text{maxevals}=0$  in NONMEM) and predictions generated, against which the model will be validated prospectively using appropriate goodness of fit tests. For example, the Anderson-Darling and Cramér–von Mises tests are accepted methods of comparing Empirical Distribution Functions for model and data (i.e., PK concentrations) to evaluate whether independent observations (i.e., observed PK concentrations from the study) are adequately described by a model (i.e., most recent population PK model).

The following will be obtained:

- A description of the key models tested during the model development will be provided and tabulated;
- Population mepolizumab plasma PK parameter estimates with 95% CI from the final model will be tabulated. Goodness of fit plots for the final model will be presented;
- Individual post-hoc PK parameter estimates (such as area under the plasma concentration-time curve over the dosing interval [AUC (0- $\tau$ )],  $C_{AV}$  [AUC (0- $\tau$ )/ $\tau$ ]) will be summarised descriptively and listed;
- Individual post-hoc predicted plasma concentrations will be summarised descriptively and listed;
- Accumulation ratio estimate will be assessed at Week 16 and 32.

The most recent model consists of a two-compartment pharmacokinetic model with first-order absorption and elimination. Bodyweight is incorporated into the model using allometry with fixed physiological allometric exponents of 0.75 and unity for clearance and volumes, respectively. Albumin and creatinine clearance are also included as covariates of mepolizumab clearance on physiological grounds, however their effects are small and not of clinical relevance. Details of the model can be found in report GlaxoSmithKline Document Number [2015N238436\\_00](#).

### 9.3.2. Investigation of Covariates

The impact of the following prospectively selected covariates on mepolizumab exposure (e.g. clearance) will be evaluated using the procedures described in Section 9.3.3.

Category	Covariates
Demographics	Weight (included in the structural model), age, race, gender, country
Baseline clinical status	Creatinine clearance, albumin (both already included in the

Category	Covariates
	current model), serum creatinine, alanine aminotransferase, aspartate aminotransferase, alkaline phosphatase, bilirubin, total protein
Baseline disease status	Flare history, blood eosinophils and baseline OCS dose
Concomitant medications	If data permits*, e.g. immunosuppressant therapies (e.g. methotrexate, azathioprine and mycophenolate mofetil), proton pump inhibitors, statins, pain relief (e.g. paracetamol, NSAIDs), interferon alfa and antihypertensive drugs
Others	Presence/absence of anti-drug antibodies and previous biologics use (monoclonal antibodies).

\*Attempt to investigate those classes of drug will be made providing data permits.

Covariate selection will be based on physiological plausibility, supported by graphical evaluation (PK parameters vs. covariates), and formally by automated linear model fitting using proc glmselect in SAS 9.2 (or higher). Individual PK parameters and covariates will be log-transformed and standardized before analysis. For forward and backward selections, significance levels of 0.1 and 0.05 will be applied respectively, in line with criteria used in previous analyses. Co-linearity between covariates will be carefully considered.

Identified covariates will then be subjected to traditional covariate analysis (with estimation step) and will follow the procedures described in Section 9.3.3. If deemed appropriate box plots of systemic clearance versus covariates of interest (e.g., immunogenicity status) will be provided.

### 9.3.3. Covariate Model Selection Procedures

The covariate model building will follow a step-wise process consisting of a forward and backward selection procedure. The likelihood ratio test will be used to evaluate the significance of incorporating or removing covariates into the population model based on alpha levels set *a priori*. For forward and backward selections, a significance level of 0.05 and 0.01 for first order conditional estimation with interaction (FOCE-I) will be used, respectively, in line with criteria used in previous analyses.

- **Step-wise forward addition procedure**

Each covariate will be included individually in the ‘base model’ to identify covariates resulting in a decrease in the objective function value (OFV) of  $> 3.84$ ,  $\chi^2 < 0.05$  for 1 degree of freedom (*df*) using FOCE-I. The retained covariates will then be added to the base model one by one, starting with the most significant ones until all covariates have been tested. Note, if a covariate exponent estimate is numerically small, the covariate will not be retained; irrespective of objective function. This will also be supported by examination of the goodness of fit. This will constitute the full model.

- **Backward elimination procedure**

From the full model, the significance of each covariate will be tested individually by removing covariates one by one until all non-significant covariates have been excluded. A covariate will be retained if upon removal, the OFV increase by more than 6.64 points ( $\chi^2 < 0.01$  for 1 *df*) using FOCE-I. Note, a covariate may be retained in the model despite being found non-statistically significant, if there is a strong rationale for its inclusion. This will constitute the final model.

Note: centering of continuous covariates may be considered, as appropriate. The mean or median value of the subjects included in the analysis may be used for example.

The impact of the presence of anti-mepolizumab antibodies may not be formally tested as a covariate in the model, considering the low incidence observed in the mepolizumab programme to date. Instead a graphical approach will be used, if deemed appropriate.

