### 13.3.2. Investigation of Covariates

The impact of the following prospectively selected plausible covariates on relevant parameters (i.e., baseline blood eosinophil count and maximum effect) will be evaluated.

Category	Covariates
Demographics	Age, race, gender
Baseline disease status	Flare history, blood eosinophils (already included in the current model)
Others	Baseline OCS absolute dose, presence/absence of anti-drug antibodies*, immunosuppressant therapies* (e.g. methotrexate, azathioprine and mycophenolate mofetil), interferon alfa*

\*Attempt to investigate those covariates will be made providing data permits.

Covariate selection will be based on physiological plausibility, supported by graphical evaluation (PD parameters vs. covariates), and formally by automated linear model fitting using proc glmselect in SAS 9.2 (or higher). Individual PD parameters and covariates will be log-transformed and standardized before analysis. For forward and backward selections, significance levels of 0.1 and 0.05 will be applied respectively, in line with criteria used in previous analyses. Co-linearity between covariates will be carefully considered.

Identified covariates will then be subjected to traditional covariate analysis (with estimation step) and will follow the same procedures as described in Section 9.3.3 for the population PK model.

Model evaluation will be as described in Section 9.3.4 for the population PK model.

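### SAP 9.3.3 gives only 1-df likelihood-ratio cut-offs (3.84 and 6.64), so its 0.05 and 0.01 levels do not hold for multi-level covariates such as race and country

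*SAP*

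**What the plan says.** SAP 9.3.3 sets the levels first: for forward and backward selection respectively, "a significance level of 0.05 and 0.01 for first order conditional estimation with interaction (FOCE-I) will be used". It then gives the working rule. In the forward step each covariate is added singly to "identify covariates resulting in a decrease in the objective function value (OFV) of" more than 3.84, labelled as the 0.05 value "for 1 degree of freedom". In the backward step, "A covariate will be retained if upon removal, the OFV increase by more than 6.64 points", labelled as the 0.01 value, again on 1 df. Both steps are worded for any covariate.

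The candidates are listed in SAP 9.3.2. The demographic row reads "Weight (included in the structural model), age, race, gender, country", and the impact of the listed covariates "will be evaluated using the procedures described in Section 9.3.3". Before that, 9.3.2 screens them on physiological plausibility, on plots, and with an automated linear model at 0.1 (forward) and 0.05 (backward). Only covariates identified there go on to 9.3.3.

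For the PKPD model, SAP 13.3.2 says that identified covariates "will follow the same procedures as described in Section 9.3.3 for the population PK model". Its demographic list has age, race and gender, but not country.

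No section says how race or country is coded in these models. Section 9.3.2 says that covariates are log-transformed and standardised, which does not define a coding for a nominal variable.

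**The concern.** Under no effect, the fall in objective function from adding a covariate follows a chi-square distribution with df equal to the number of parameters added. For a nominal covariate with m levels that is m − 1. The values 3.84 and 6.64 are the 5% and 1% points only when one parameter is added. For a covariate with more, the stated level and the stated cut-off cannot both apply, and the cut-off is too easy to exceed.

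A stated purpose of these models (SAP 9.3 and 13.3) is to identify sources of between-subject variability. A chance effect of race or country on clearance, or of race on eosinophil response, could be reported as meeting a 1% criterion that it did not meet. It could also enter the final model. SAP 9.3.1 takes individual exposures from the PK modelling, and SAP 14.2 uses model-estimated clearance in the exploratory exposure-response analysis.

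**Working it through.** **Inputs**
- Levels 0.05 and 0.01, cut-offs 3.84 and 6.64, 1 df: SAP 9.3.3.
- Race: four categories in the efficacy subgroup table, SAP 5.4.2. That gives 4 − 1 = 3 df if the PK models use the same coding (assumption).
- Country: the number is not stated. SAP 5.3 names the USA, Argentina, Mexico and Brazil, plus Rest of World. That gives at least 5 levels, so at least 4 df, if all enrol (assumption).
- Sample size: 40 per arm planned (Protocol 9.2.1), up to 60 (Protocol 9.2.3). The PK population needs a measurable concentration, so I take it as roughly the mepolizumab arm.

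**Step 1. Reproduce the plan's figures.** The 1-df critical values are 1.960² = 3.84 and 2.576² = 6.635. Tail areas: P(χ²₁ > 3.84) = 0.0500 and P(χ²₁ > 6.64) = 0.0100. The cut-offs are right for one parameter.

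**Step 2. Actual level of each step for k parameters,** P(χ²ₖ > 3.84) and P(χ²ₖ > 6.64), beside the correct critical values:

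| df | forward, > 3.84 | backward, > 6.64 | correct 0.05 / 0.01 cut-off |
|---|---|---|---|
| 1 | 5.0% | 1.0% | 3.84 / 6.63 |
| 2 | 14.7% | 3.6% | 5.99 / 9.21 |
| 3 (race, 4 levels) | 27.9% | 8.4% | 7.81 / 11.34 |
| 4 (5 countries) | 42.8% | 15.6% | 9.49 / 13.28 |
| 7 (8 countries) | 79.8% | 46.7% | 14.07 / 18.48 |

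**Step 3. Allow for the screen in 9.3.2.** I used a linear-model analogue: a normal outcome with no covariate effect, equally likely levels and 40,000 simulated data sets. A (levels − 1)-df F test at 0.05 (or 0.1) stands for the screen, followed by a likelihood-ratio statistic above 6.64. Results for 40 subjects:

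| levels | LRT > 6.64 alone | 0.05 screen, then > 6.64 | 0.1 screen, then > 6.64 | 0.05 screen, then correct 1% cut-off |
|---|---|---|---|---|
| 2 | 1.2% | 1.2% | 1.2% | 1.2% |
| 4 | 11.4% | 5.1% | 10.4% | 1.7% |
| 5 | 20.4% | 5.0% | 10.0% | 1.8% |
| 8 | 57.1% | 5.1% | 10.1% | 2.7% |

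With 60 subjects the 0.05-screen figures are 4.9%, 5.1% and 4.7% for 4, 5 and 8 levels. They fall to 1.4%, 1.4% and 1.8% with the correct cut-off. The residual excess over 1% is a small-sample effect of the chi-square approximation.

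**Step 4. Why the backward step does so little.** In this analogue, with d = levels − 1, the likelihood-ratio statistic is n × ln(1 + dF/(n − d − 1)). At the 0.05 boundary of the F test with n = 40:
- d = 3, F = 2.866: 40 × ln(1 + 3 × 2.866/36) = 8.57, already above 6.64.
- d = 2, F = 3.252: 40 × ln(1 + 2 × 3.252/37) = 6.48, just below 6.64.

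For four or more levels, anything that passes the 0.05 screen has therefore cleared 6.64 already, and the 0.01 step removes nothing. For three levels it still removes a little.

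**The case against.** **The cut-offs are labelled as 1-df values and the levels are set separately, so an analyst could apply the stated level at the df of the term.** That is possible, and it is why this is a gap rather than an instruction to misuse the test. But the rule is worded for any covariate, no other cut-off is given, and the list sent to it contains race and country.

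**The df are assumed.** This stands. The four race categories come from an efficacy table that allows categories to be collapsed, and the number of countries is not given. If either covariate is reduced to two levels, 3.84 and 6.64 are correct. The SAP does not say that it will be.

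**The screen comes first.** This also stands. A reader of the Step 2 table might infer that race or country would be retained by chance far more often than both 5% and 1%. The documents do not support that. The 3.84 cut-off governs entry, not final retention, and a screen with a 0.05 stay level holds the overall rate near 5%. Nor does every multi-level covariate that passes the screen exceed 6.64 automatically: three levels are an exception, and the later step uses a different likelihood (FOCE-I on concentrations) from the linear screen. If the screen splits a nominal covariate into single indicators, each of those tests has 1 df.

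**Other filters apply.** Plausibility, plots, co-linearity, goodness of fit and the removal of numerically small effects may each discard a false positive. They rest on judgement without numeric limits. Section 9.3.3 also lets a non-significant covariate stay if there is a strong rationale. None of this makes the cut-offs right for a multi-parameter term.

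**Conclusion.** The point holds as a gap in the selection rule. Section 9.3.3 states levels of 0.05 and 0.01 but gives cut-offs that deliver them only for single-parameter covariates. At 3 df the steps run at 27.9% and 8.4%, and at 4 df at 42.8% and 15.6%. Through the whole sequence, chance retention is about 5%, or up to about 10% if only the screen's 0.1 entry level governs, against a stated 1%.

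The step-level figures depend on the assumed coding. The sequence figures depend on the linear-model analogue, equal level probabilities, a multi-df screen and about 40 subjects. They leave out the judgement-based filters, so they are not the exact error rates of the written procedure.

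The reach is limited. Race is affected in the population PK and PKPD models. Country is affected in the population PK model only. The PKPD and exposure-response analyses are themselves conditional on being deemed appropriate. The primary and secondary efficacy tests do not use this selection.

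**What to change.** In SAP 9.3.3, and so by reference in 13.3.2, state the criterion as the chi-square critical value at 0.05 (forward) and 0.01 (backward), with df equal to the number of parameters added or removed: 5.99 / 9.21 for 2 df, 7.81 / 11.34 for 3 df, 9.49 / 13.28 for 4 df. Keep 3.84 / 6.64 for single-parameter covariates.

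State how race and country are coded, including any grouping of sparse levels. Grouping country into the three randomisation regions of SAP 5.3, for example, would be a 2-df term.

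This takes a sentence or two and no new data. The one downside is that a real multi-level effect needs a larger likelihood gain to be kept, which the levels already stated imply.

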#### **9.3.4. Model Evaluation**

The uncertainty in the parameter estimates will be assessed (e.g. from the standard error estimates provided by NONMEM or from the 95% CI estimates provided by other appropriate analysis conducted using other software). Furthermore, the model performance will be investigated using a set of goodness of fit plots as well as Visual Predictive Check (VPC) method. Other evaluation methods may be used (e.g., bootstrapping) if deemed appropriate.

## 10. PHARMACODYNAMIC ANALYSES

### 10.1. Blood Eosinophils

#### 10.1.1. Population of Interest

Blood eosinophil analyses will be based on the Pharmacodynamic population.

#### 10.1.2. Endpoint / Variables

Absolute and ratio to baseline blood eosinophil counts at each visit. For blood eosinophils, baseline will be defined as the latest blood eosinophil value measured by the central laboratory prior to the first dose of study treatment.

#### 10.1.3. Summary Measure

The difference between mepolizumab and placebo in the ratio to baseline of blood eosinophils.

#### 10.1.4. Strategy for Intercurrent (Post-Randomization) Events

For subjects withdrawing prematurely from study treatment, only the endpoint values up to and including 28 days after the last dose of study treatment will be included in the analysis ('while on treatment' estimand).

#### 10.1.5. Statistical Analyses / Methods

- Blood eosinophil counts will be  $\log_e$ -transformed prior to analysis. Non-detectable blood eosinophil values of 0 GI/L, or results below the limit of quantification will be replaced by half of the lowest observed detectable (non-zero) value in the study data set, prior to log transformation.
- Absolute and ratio to baseline blood eosinophil counts will be summarised by treatment group and visit. Only results from the central laboratory will be included in the summary, however all data will be listed.
- Full details of data displays to be presented are given in [Appendix 10: List of Data Displays](#).

##### 10.1.5.1. Statistical Methodology Specification

Endpoint

 
• Ratio to baseline blood eosinophil count
 

Model Specification

 
• A mixed effects repeated measures model will be fitted to the <math>\log_e</math> transformed blood eosinophil data with the following specification:             
 
• Visit, treatment and region included as fixed categorical effects.
 
 
 

 
• Baseline blood eosinophil count (<math>\log_e</math> scale) and baseline OCS dose included as continuous fixed covariates.
 
• Interaction terms for baseline (screening) blood eosinophil count-by-visit and treatment-by-visit.
 
• The Kenward and Roger method (DDFM = KR) for approximating the denominator degrees of freedom to correct for bias in the estimated variance-covariance matrix.
 
• REPEATED statement with TYPE=UN to specify an unstructured covariance structure for the R matrix.
 
• The OBSMARGIN option on the LSMEANS statement in order to compute the adjusted geometric means with weights proportional to the input data set.
 

Model Results Presentation

 
• Number analysed in each treatment group.
 
• LS Mean (SE) and LS Mean ratio to screening (SE) in each treatment group.
 
• Mean treatment ratio, 95% CI and p-value for mepolizumab vs placebo.
 

Subgroup Analyses

 
• No subgroup analyses will be performed on this endpoint.
 

Sensitivity and Supportive Statistical Analyses

 
• The MMRM model specified above will also be fitted to the log transformed absolute blood eosinophil counts and adjusted mean absolute blood eosinophil counts and 95% CI from this model will be plotted.
 

## 10.2. Serum Total IL-5

### 10.2.1. Population of Interest

Total IL-5 analyses will be based on the Pharmacodynamic population.

### 10.2.2. Endpoint / Variables

Absolute and ratio to baseline total IL-5 at Week 32

### 10.2.3. Summary Measure

The difference between mepolizumab and placebo in the ratio to baseline of serum total IL-5 at Week 32.

### 10.2.4. Strategy for Intercurrent (Post-Randomization) Events

For subjects withdrawing prematurely from study treatment, only the endpoint values up to and including 28 days after the last dose of study treatment will be included in the analysis ('while on treatment' estimand).

### 10.2.5. Statistical Analyses / Methods

- Total IL-5 values will be  $\log_e$ -transformed prior to analysis. Values below the limit of quantification will be replaced by half the limit of quantification, prior to log

transformation. Summary statistics will include the number and percentage of BLQ values.

- Absolute and ratio to baseline total IL-5 values will be summarised by treatment group and visit (Baseline and Week 32).
- Full details of data displays to be presented are given in [Appendix 10: List of Data Displays](#).

